1. INTRODUCTION

The purpose of this reporting and analysis plan (RAP) is to describe the analyses to be included in the CSR for Protocol: 213055.

Revision Chronology:		
Original Protocol 213055	25-MAR-2021	Original
Amendment 1	05-MAY -2021	

2. SUMMARY OF KEY PROTOCOL INFORMATION

This study will compare the relative bioavailability (BA) of 2 Fixed-Dose Combinations (FDCs) of GSK3640254 / Dolutegravir (DTG) with GSK3640254 and DTG administered together as single agents (Part 1). In addition, this study will investigate the effect of food on the pharmacokinetics (PK) of the selected FDC of GSK3640254 / DTG. This study will investigate the effect of a high fat and calorie meal on the PK, safety, and tolerability of the FDC of GSK3640254 + DTG, in comparison with administration under fasting conditions (Part 2).

2.1. Changes to the Protocol Defined Statistical Analysis Plan

Changes from the originally planned statistical analysis specified in the protocol are outlined in Table 1.

Table 1 Changes to Protocol Defined Analysis Plan

Protocol	Reporting & Analysis Plan	
Statistical Analysis Plan	Statistical Analysis Plan	Rationale for Changes

 This is an open-label study 	
 Biostatistics and Programming teams from both GSK and PPD will remain blinded to the actual randomization schedule. Other teams including PPD Clinical Pharmacology team will remain open-label 	
 Biostatistics and Programming teams remain blinded following GSK's requirement

2.2. Study Objective(s) and Endpoint(s)

Objectives	Endpoints
Primary	
Part 1 
 To assess the relative BA of FDCs of GSK3640254 / DTG compared with GSK3640254 / DTG administered together as single agents when administered with a moderate fat and calorie meal Part 2 
 To assess the effect of food on the PK of the selected FDC of GSK3640254 / DTG when administered with a high fat and calorie meal compared to fasted conditions 	Parts 1 and 2 
 Plasma AUC(0-∞), AUC(0-t), and Cmax for GSK3640254 and DTG
Secondary	
Part 1 
 To assess the safety and tolerability of FDCs of GSK3640254 / DTG compared with GSK3640254 and DTG administered together as single agents 	Parts 1 and 2 
 Safety and tolerability parameters for AEs or SAEs, observed and change from baseline clinical laboratory assessments, ECGs, and vital sign measurements

Objectives	Endpoints
Part 2 
 To assess the safety and tolerability of selected FDC of GSK3640254 / DTG following single oral administration to healthy participants under fasted or fed conditions 	

2.3. Study Design

Overview of Study Design and Key Features	
Figure 1 Study Design Schematic	
FDC = fixed dose combination; WO = washout	
Design Features	
A Phase 1, 2-part, randomized, open-label, crossover study. The study will consist of a screening period and a treatment period.
 
 Screening Period: within 28 days before the first dose of study intervention 
 Part 1: 3-period, 3-treatment, crossover design, with a washout period of at least 7 days (-4 hours) between doses Part 2: 2-period, 2-treatment crossover design, with a washout period of at least 7 days (-4 hours) between doses
Dosing	
 Part 1: 
 Treatment A = A single oral dose of GSK3640254 25 mg (2 x tablets), GSK3640254 100 mg (1 x tablet) and DTG 50 mg (1 x tablet) administered together under moderate fat and calorie conditions Treatment B = A single oral dose of GSK3640254 / DTG, 150 mg / 50 mg (1 x monolayer tablet) FDC administered under moderate fat and calorie conditions. Treatment C = A single oral dose of GSK3640254 / DTG, 150 mg / 50 mg (1 x bilayer tablet) FDC administered under moderate fat and calorie conditions. Part 2: 
 Treatment D = A single oral dose of selected FDC of GSK3640254 / DTG, 150 mg / 50 mg administered under high fat and calorie conditions Treatment E = A single oral dose of selected FDC of GSK3640254 / DTG, 150 mg / 50 mg administered under fasted conditions
Time & Events	
 Refer to Appendix 1: Schedule of Activities
Treatment Assignment	
 This is a randomized study. Biostatistics and Programming teams from both GSK and PPD will remain blinded to the actual randomization schedule. Other teams including PPD Clinical Pharmacology team will remain open-label.

Overview of Study Design and Key Features	
	
 • In Part 1, participants will be randomly assigned to 1 of 3 treatment sequences in 1:1:1 ratio; in Part 2, participants will be randomly assigned to 1 of 2 treatment sequences in 1:1 ratio. • Site pharmacy group will use a computer-generated randomization schedule for treatment assignments. • The computer-generated randomization schedule will be produced by SAS software (Version 9.4).
Interim Analysis	
 • After completion of Part 1 the study, preliminary safety & PK data will be analyzed by PPD under the oversight of Clinical Pharmacology Modeling & Simulation within VH/GSK to determine the formulation to be used in Part 2. • GSK Clinical Pharmacology Modeling and Simulation and the study team will inform the principal investigator of the formulation decision. • The interim outputs will be produced by WinNonlin (8.0 or higher).

2.4. Statistical Hypotheses

There is no formal research hypothesis that will be statistically tested in this study.

2.5. Sample Size

As there is no formal research hypothesis being statistically tested in this study, the sample size was not selected based on statistical considerations but determined using feasibility. For each part, approximately 18 participants will be enrolled to ensure that 14 evaluable participants complete the study. If participants prematurely discontinue the study, additional participants may be enrolled after consultation with the sponsor to ensure that the required number of evaluable participants complete the study.

Since it was expected that coadministration of GSK3640254 and DTG would increase the exposure of DTG, ranges for point estimate for a ratio of 1.0, 1.1, and 1.2 were explored. It was expected that coadministration of GSK3640254 with DTG would have no significant impact on the exposure of GSK3640254, thus ranges for point estimate for a ratio of 0.9, 1.0, and 1.1 were explored. The details of the results of these analyses can be found in the protocol Section 9.2.

2.6. Study Blinding

The Biostatistics and Programming teams for GSK will be blinded during this study. PPD will work with ADaM datasets and table, listing, and figures (TLFs) based on the surrogate randomization schedule, and not having access to the actual randomization schedule until unblinding process in the final analysis.

Once Medidata RaveDatabase Hard Lock occurs, Source Data Lock is achieved, at which point the PPD team will switch from surrogate to actual randomization. The unblinded SDTM datasets will be transferred to the GSK Data Management team, who will authorize Database Freeze (DBF). At this point the entire GSK study team is officially unblinded.

3. PLANNED ANALYSES

3.1. Interim Analyses

There is no formal interim analysis planned but an analysis using preliminary PK data from Part 1 will be used to determine the formulation to be used for Part 2.

GSK Clinical Pharmacology Modeling and Simulation and the study team will inform the principal investigator of the formulation decision.

The interim outputs will be produced by WinNonlin (8.0 or higher).

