Part 2 will be dosed using a formulation selected from Part 1 based on PK data. Treatment D will be administered in the fed state. Participants will fast overnight for at least 10 hours prior to breakfast and will receive a high fat and calorie meal 30 minutes

prior to dosing. Participants will eat this meal in 25 minutes or less. Dose administration will occur within 5 minutes of completion of meal consumption. Participants will not receive any further food until 4 hours after dosing. Treatment E will be administered in the fasted state. Participants will fast overnight for at least 10 hours prior to dosing and until 4 hours after dosing.

In both Part 1 and Part 2, PK blood samples for the analysis of GSK3640254 and DTG will be collected prior to dosing (0 hour) on Day 1 and up to 96 hours post-dose in each period.

Safety and tolerability will be assessed by monitoring and recording of adverse events (AEs) and serious AEs (SAE), clinical laboratory test results, vital sign measurements, 12-lead electrocardiogram (ECG) results, and physical examination findings.

Study assessments will be performed as indicated in the Schedule of Activities (SoA; Section 1.3). For Part 1, study participants will be confined to the clinic from Day -2 of Period 1 until discharge on Day 5 of Period 3. For Part 2, study participants will be confined to the clinic from Day -2 of Period 1 until discharge on Day 5 of Period 2.

Brief Summary: A relative BA and food-effect study of the FDC of GSK3640254 / DTG in healthy participants. Study details include:

Part 1:

- Study Duration: 56 days (including screening)
- Treatment Duration: 3 days (Day 1 of each period)

Part 2:

- Study Duration: 49 days (including screening)
- Treatment Duration: 2 days (Day 1 of each period)

Number of Participants: For each part, approximately 18 participants will be enrolled to ensure that 14 evaluable participants complete the study.

Note: "Enrolled" means a participant's, or their legally acceptable representative's, agreement has been obtained to participate in a clinical study following completion of the informed consent process and screening. Potential participants who are screened for the purpose of determining eligibility for the study, but do not participate in the study, are not considered enrolled, unless otherwise specified by the protocol.

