6.1. Study Interventions Administered

In Part 1, all 3 treatments will be administered as per randomized treatment sequence. Based on Part 1 interim analysis, a treatment will be selected for administration in Part 2.

| Treatment | A | A | B | C |
|-------------------|------------|--------|-------------------------------|-------------------------------|
| Intervention Name | GSK3640254 | DTG | GSK3640254 / DTG (GSK4107821) | GSK3640254 / DTG (GSK4107821) |
| Type | Drug | Drug | Drug | Drug |
| Dose Formulation | Tablet | Tablet | Tablet | Tablet |

| Treatment | A | A | B | C |
|--------------------------------|---|--|---|---|
| Unit Dose Strength(s) | GSK3640254 25mg, 100 mg | DTG 50 mg | GSK3640254 / DTG, 150 mg/50 mg | GSK3640254 / DTG, 150 mg/50 mg |
| Dosage Level(s) | Single dose of 2 x GSK3640254 25mg Tablets + 1 x GSK3640254 100mg Tablet | DTG 50 mg | Single dose of 1 x GSK3640254 / DTG Tablet | Single dose of 1 x GSK3640254 / DTG Tablet |
| | Administered together as a single dose | | | |
| Route of Administration | Oral | Oral | Oral | Oral |
| Use | Experimental | Experimental | Experimental | Experimental |
| IMP and NIMP | IMP | IMP | IMP | IMP |
| Sourcing | GSK3640254 Sourced by Sponsor | DTG Sourced Locally | GSK3640254 / DTG Sourced by Sponsor | GSK3640254 / DTG Sourced by Sponsor |
| Packaging and Labeling | Provided in bulk by GSK. The investigator will package in high density polyethylene bottles. Each bottle will be labeled as required per country requirement. | 30 tablets in a HDPE bottle labelled per country requirement | Provided in bulk by GSK. The investigator will package in high density polyethylene bottles. Each bottle will be labeled as required per country requirement. | Provided in bulk by GSK. The investigator will package in high density polyethylene bottles. Each bottle will be labeled as required per country requirement. |

DTG = dolutegravir; FDC = fixed-dose combination; IMP = investigational medicinal product; NIMP = non investigational medicinal product.

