9.4. Statistical Analyses

The statistical analysis plan will be finalized prior to database lock and it will include a more technical and detailed description of the statistical analyses described in this section. This section is a summary of the planned statistical analyses of the most important endpoints including primary and key secondary endpoints.

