9.5. Interim Analysis

There will be no formal interim analysis. An analysis is planned after completion of Part 1 and will inform FDC formulation to include in Part 2. Preliminary safety & PK data will be analyzed by PPD under the oversight of Clinical Pharmacology Modeling & Simulation within VH/GSK.

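### Does the plan need a stated rule for choosing the Part 2 formulation before Part 1 results are seen?

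*SAP*

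**What the plan says.** Five places describe the selection.

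- Protocol 1.1 (Synopsis): "Part 2 will be dosed using a formulation selected from Part 1 based on PK data".
- Protocol 6.1: "Based on Part 1 interim analysis, a treatment will be selected for administration in Part 2".
- Protocol 9.5: "An analysis is planned after completion of Part 1 and will inform FDC formulation to include in Part 2". It adds that preliminary safety and PK data will be analysed.
- SAP 2.3, Interim Analysis row: "preliminary safety & PK data will be analyzed by PPD", for the purpose of determining the Part 2 formulation.
- SAP 3.1: "an analysis using preliminary PK data from Part 1 will be used to determine the formulation to be used for Part 2".

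Both SAP sections also name the software and say who tells the investigator of the decision. None of the five gives a deciding analyte, parameter, threshold or tie-break.

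The primary endpoints in SAP 2.2 are AUC(0-∞), AUC(0-t) "and Cmax for GSK3640254 and DTG", so three parameters for each of two analytes. Protocol 9.4.1 and SAP 7.1.4.1 specify B versus A and C versus A for each, with 90% confidence intervals, and SAP 5.1 labels A as the reference. Protocol 9.1 and SAP 2.4 state that no hypothesis is tested.

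**The concern.** The choice between B and C is the study's one decision driven by its own data. Two teams working from the same documents and the same Part 1 results could take different tablets forward, and only the chosen one gets a food-effect estimate.

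Timing adds to the unease. Protocol 9.4 says "The statistical analysis plan will be finalized prior to database lock", which is later than the selection, and SAP 2.1 says "Other teams including PPD Clinical Pharmacology team will remain open-label". So nothing visible requires the basis to be fixed before results by treatment are known. The SAP also appears to disagree with itself on whether safety data enter the choice. At stake is whether the report can show that the selection followed a criterion set beforehand, in a study meant to inform formulation decisions.

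**Working it through.** **1. Which wordings conflict.** Protocol 1.1 and SAP 3.1 rest the choice on PK data. SAP 2.3 has safety and PK data determine it. Protocol 9.5 has both analysed and lets the analysis inform the choice, which fits either reading. The only real clash is SAP 2.3 against SAP 3.1 and the Synopsis. The natural reading is that PK decides and safety is checked before a new group is dosed.

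**2. What is already defined.** The Part 1 objective (relative bioavailability against the single agents), the reference, the parameters and both contrasts are all stated. What is missing is the link from these to the selection, and an order of priority.

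**3. What the selection can affect.**
- Part 1: both contrasts are estimated for all six endpoints and shown in Table 3.13 and Figure 3.17 whichever tablet is chosen, so nothing is reported selectively.
- Part 2: exclusion criterion 24 bars prior GSK3640254 exposure, so the participants are new. The D versus E estimate does not reuse the data that drove the choice.
- Error rates: there is no test, so there is no type I error to protect.

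**4. Precision available for the choice.** The protocol's half-width (Section 9.2.1) is reproduced by t(0.95, N−1) × σw × √(2/N), with σw = √ln(1 + CVw²). At N = 14:
- DTG, CVw 21%: 1.771 × 0.2077 × 0.3780 = 0.139 (stated 0.139).
- GSK3640254, CVw 27.2%: 1.771 × 0.2672 × 0.3780 = 0.179 (stated 0.179).

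B against C within participant has the same precision. A true ratio of 0.90 is 0.105 on the log scale, inside both half-widths.

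**5. How often a fully stated rule misses.** Take the rule: choose the tablet whose estimated ratio to A is nearer 1. Let the true ratios be B/A = 0.90 and C/A = 1.0, and δ = −ln 0.90 = 0.1054. B is chosen when log(C/A) − log(B/A) and log(C/A) + log(B/A) have the same sign. These are uncorrelated, with means δ and −δ and standard errors σw√(2/N) and σw√(6/N). So

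P(choose B) = Φ(δ/σw√(2/N)) × Φ(−δ/σw√(6/N)) + Φ(−δ/σw√(2/N)) × Φ(δ/σw√(6/N)).

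- GSK3640254: standard errors 0.1010 and 0.1749, so 0.852 × 0.273 + 0.148 × 0.727 = 0.34.
- DTG: standard errors 0.0785 and 0.1360, so 0.910 × 0.219 + 0.090 × 0.781 = 0.27.

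**6. How much is the missing rule and how much is noise.** If the analytes are independent within participant, the two single-analyte rules disagree in 0.34 × 0.73 + 0.27 × 0.66 = 0.43 of studies. Simulation gives 43%, 38% and 31% for between-analyte correlations of 0, 0.3 and 0.6 (assumed; the documents give none). In this scenario both rules aim at the same tablet, so every disagreement is sampling error in one of them.

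Two complete rules were also compared: GSK3640254 AUC(0-∞) nearest 1, and smallest total distance from 1 over all six endpoints. The correlations were assumed: AUC with Cmax 0.5 to 0.8, between analytes 0 to 0.6, and the two AUCs 0.98.

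| True B/A (C/A = 1.0) | The two rules pick different tablets |
|---|---|
| 1.00 | 21–26% |
| 0.90 | 18–24% |
| 0.80 | 8–10% |

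In the first row the tablets are identical, so disagreement has no PK consequence. In the last row the rules mostly agree.

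**The case for a change.** The strongest case for a change is that a rule costs one SAP paragraph and that rules can differ by more than the table shows. On GSK3640254 AUC(0-∞), choosing the tablet nearest to A and choosing the one with the highest exposure disagree in about 27% of studies at a true B/A of 0.90, and those rules have different aims. SAP 3.2 starts the final analyses only after all participants finish, and SAP 11.9.3 lists a single final deliverable, so no selection output is specified. Requiring only stated inputs would still leave the judgement with the sponsor.

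Part of this stands. The link from the Part 1 contrasts to the choice is unwritten, and SAP 2.3 and SAP 3.1 differ. The rest does not carry. Part 1 is framed as bioavailability relative to A, which makes closeness to A the ordinary reading; no document suggests maximising exposure. If the two analytes truly favour different tablets, weighing them is a development judgement, and nothing in the documents shows that one ranking is statistically better. Any rule would have to be supplied by the sponsor, who already owns the decision.

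The timing argument is an inference: the SAP's approval date is not visible in the public text, and database lock is only the latest date allowed. Rewording the Protocol sections would be an amendment needing ethics approval under Protocol 10.1.1, for no change in any result.

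**Conclusion.** No change to the plan is needed. The missing detail concerns an internal formulation choice in a Phase 1 study with no hypothesis and a sample size set by feasibility. It leaves the B/A and C/A ratios and the Part 2 food-effect estimate intact, and both sets of ratios will be on view for anyone judging the choice.

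A written rule would improve traceability but would do little for the reliability of the selection. At N = 14, a single-analyte rule picks the tablet further from the reference in about 34% (GSK3640254) or 27% (DTG) of studies at a true ratio of 0.90. Two reasonable complete rules differ in about a fifth of studies there, and in 8–10% at a true ratio of 0.80.

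These figures rest on the protocol's CVw of 27.2% and 21%, which it calls conservative, on equal true ratios for both analytes and, for the comparison of rules, on assumed correlations. The mismatch over safety data is a wording slip that the study team can resolve without touching an analysis.

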3.2. Final Analyses

The final planned primary analyses will be performed after the completion of the following sequential steps:

1. All participants have completed the study as defined in the protocol.
2. All required database cleaning activities have been completed and final database release (DBR).
3. All criteria for unblinding the randomization codes have been met.
4. Randomization codes have been distributed by the PPD Randomization Team to PPD Biostatistics and Programming team.
5. Database freeze has been declared by GSK Data Management after reviewing the unblinded SDTM datasets.
6. Only after DBF has been declared by GSK Data Management can GSK Biostatistics and Programming be unblinded.

4. ANALYSIS POPULATIONS

Population	Definition / Criteria	Analyses Evaluated
Screened	
 • All participants who signed the informed consent form • This population will be used for screen failure listing and summary. 	
 • Study Population
Enrolled	
 • All participants who passed screening and entered the study. • This population will be used for summary of enrolled participants 	
 • Study Population
Randomized	
 • All participants who were randomly assigned to a treatment sequence. • This population will be used for listing of randomization schedule. 	
 • Study Population
Safety	
 • All participants who received at least one dose of study intervention. • This population will be used for the safety displays and baseline/demographic characteristics. 	
 • Study Population • Safety
Pharmacokinetic Concentration	
 • All participants who underwent plasma PK sampling and had evaluable PK assay results. • This population will be used for the PK concentration listings, summary tables, and plotting of concentration-time data. 	
 • PK Concentration
Pharmacokinetic Parameter	
 • All participants who underwent plasma PK sampling and had evaluable PK parameters estimated. • This population will be used for PK parameter listings, PK parameter summary tables, and statistical analysis tables. 	
 • PK Parameter • PK statistical analysis

Refer to Appendix 9: List of Data Displays which details the population used for each display.

4.1. Protocol Deviations

Important protocol deviations (including deviations related to study inclusion/exclusion criteria, conduct of the trial, patient management, or patient assessment) will be summarized and listed.

Protocol deviations will be tracked by the study team throughout the conduct of the study in accordance with the Protocol Deviation Management Plan. The “significant” protocol deviation in the Protocol Deviation Management Plan is equivalent to “important” protocol deviations.

- Data will be reviewed prior to unblinding and freezing the database to ensure all significant deviations [and deviations which may lead to exclusion from the analysis populations] are captured and categorized on the protocol deviations dataset.
- This dataset will be the basis for the summaries and listings of protocol deviations.

A separate listing of all inclusion/exclusion criteria deviations will also be provided. This listing will be based on data as recorded on the inclusion/exclusion page of the electronic case report form (eCRF).

5. CONSIDERATIONS FOR DATA ANALYSES AND DATA HANDLING CONVENTIONS

5.1. Study Treatment & Sub-group Display Descriptors

Treatment Group Descriptions		
Data Displays for Reporting – Part 1		
By Treatment		
Description	Code	Order in TLF
A single oral dose of GSK3640254 25 mg (2 x tablets), GSK3640254 100 mg (1 x tablet) / DTG 50 mg (1 x tablet) administered together under moderate fat and calorie conditions (reference)	Treatment A	1
A single oral dose of GSK3640254 / DTG, 150 mg / 50 mg (1 x monolayer tablet) FDC administered under moderate fat and calorie conditions	Treatment B	2
A single oral dose of GSK3640254 / DTG, 150 mg / 50 mg (1 x bilayer tablet) FDC administered under moderate fat and calorie conditions	Treatment C	3
By Sequence		
Description	Code	Order in TLF
Sequence 1	ABC	1
Sequence 2	BCA	2
Sequence 3	CAB	3
Data Displays for Reporting – Part 2		
By Treatment		
Description	Code	Order in TLF
A single oral dose of selected FDC from Part 1 of GSK3640254 / DTG, 150 mg / 50 mg administered under high fat and calorie conditions	Treatment D	1
A single oral dose of selected FDC from Part 1 of GSK3640254 / DTG, 150 mg / 50 mg administered under fasted conditions	Treatment E	2
By Sequence		
Description	Code	Order in TLF
Sequence 1	DE	1
Sequence 2	ED	2

